4 will be performed to permit retrospective determination of the characteristics of an effective product and
5 dosage regimen, and the characteristics of patients most likely to benefit¹⁸.

6 Data and blood specimen will be banked for future use pursuant to the IRB Approved Inova COVID-19
7 Biobanking Protocol. We will follow the guidelines and procedures for specimen storage and access as
8 described in the IRB approved Inova COVID-19 Biobanking Protocol.

9 Specimens will be stored at the Office of Research at Inova Biobank with standard certifications in place.

10

1 **PLASMA RECIPIENTS:**

2 **Inclusion Criteria for Recipients of COVID-19 Convalescent Plasma:**

3 Patients in the Inova Health System with confirmed COVID-19 by PCR testing

4 Age \geq 13 years

5 Currently hospitalized with COVID-19 infection with severe or life-threatening clinical syndrome²² as
6 follows:

7 Severe COVID-19: (three or more of the following)

8

- 10 • Dyspnea
- 11 • Respiratory rate \geq 30/min
- 12 • Blood oxygen saturation (SpO₂) \leq 94% on room air
- 13 • Partial pressure of arterial oxygen to fraction of inspired oxygen (P:F) ratio $<$ 300
- 14 • Pulmonary infiltrates $>$ 50% of lung parenchyma within 24 to 48 hours

15 Life-threatening disease is defined as: (one of the following)

- 16 • Respiratory failure
- 17 • Septic shock, and/or
- 18 • Multiple organ dysfunction or failure

19 Patient must provide informed consent or have health care power of attorney/next of kin provide consent
20 if he/she cannot.

21 **Exclusion Criteria:**

22 Contraindication to receive plasma as deemed by the treating physician

23 Severe hypercoagulable state (documented in medical chart or by treating physician assessment)

24 Absolute IgA deficiency

25 Prior history of Transfusion Related Acute Lung Injury (TRALI)

26 Inability to tolerate plasma volume due to severe systolic or diastolic heart failure despite slower infusion
27 and diuretic administration

28 Positive pregnancy test (HCG)

29 **Recipient Screening Labs**

30 Blood Type

31 Total immunoglobulin (Ig) levels: IgG, IgA, IgM

32 Coagulation tests to include PT/INR and PTT

33 Complete blood count and differential

34 **Pre-Treatment Testing:**

35 Optional Blood draw for Inova COVID-19 Biobank (up to four tubes each) prior to each dose of plasma

36 **Target Recipient Recruitment:** 150-200 individuals

37 **Primary Endpoints:**

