21 transformations explored as needed. All analyses will be conducted using SAS (version 9.4, Cary, NC)
22 with p<0.05, two-tailed considered statistically significant.

23
24 Primary efficacy endpoints:

25 1. Gilead 7-point scale – For each time point (day 0 vs. 7), summary clinical status scores will be
26 calculated. Changes in scores will be subsequently assessed via a generalized linear mixed model
27 with clinical status assessed at day 0 vs. 7. A statistically significant increase of ± 2 points in β
28 from day 0 to day 7 will be considered as evidence of efficacy. A mixed model allows for
29 examination and inclusion of the variance-covariance matrix into the model as a result of expected
30 within-subject serial correlation as a result of repeated assessments over time.
31 2. Plasma transfusion related adverse events will be scored as 1+ vs. 0 and will be assessed via Chi-
32 Square test with a hypothesized distribution of expected AE (using the higher incidence estimate):
33 i. Transfusion Associated Circulatory Overload: 1:1,566 to 1:68 plasma units
34 transfused
35 ii. Transfusion-Related Lung Injury: 1:1,200 to 1:190,000
36 iii. Allergic Reaction/Anaphylaxis: 1-3%
37 iv. Febrile Transfusion Non-hemolytic Transfusion Reaction: 0.1-1%

38
39 Secondary endpoints:

40 1. Change in 7-point ordinal scale score and SOFA score over time will be assessed via individual
41 growth models (IGM). Times will be day0, 14, 21, and 28
42 2. Mortality will be assessed via Chi-Square test with a hypothesized current mortality rate of 1-5%
43 (age adjusted).
44 3. Need for mechanical ventilation for those not ventilator at time of plasma infusion will be
45 assessed via Chi-Square test with a currently available published estimates.

1 4. Time to discontinuation of supplemental oxygen, time to liberation from mechanical ventilation,
2 duration of hospitalization will be summarized as median (IQR) or rates and compared to currently
3 available published estimates.
4
5

6 **ADVERSE EVENTS AND TOXICITY MANAGEMENT**

7 **Definitions of Adverse Events and Serious Adverse Events**

9 **Adverse Events (AE)**

10 An AE is any untoward medical occurrence in a clinical study subject administered an investigational
11 product, which does not necessarily have a causal relationship with the treatment. An AE can therefore be
12 any unfavorable and/or unintended sign, symptom, or disease temporally associated with the use of an

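### One unadjusted p<0.05 label covers every analysis, so safety and secondary results can be called significant on the same footing as the single test that carries the efficacy rule

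*Combined protocol and SAP*

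**What the plan says.** The opening paragraph of the Statistical Plan sets the rule for the whole study: "All analyses will be conducted using SAS (version 9.4, Cary, NC"), "with p<0.05, two-tailed considered statistically significant". The analyses that follow are:

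- **Primary, item 1:** a mixed model of the 7-point scale, day 0 against day 7. This is the only analysis with a success rule: "A statistically significant increase of ± 2 points in β" between those days counts as evidence of efficacy.
- **Primary, item 2:** "Plasma transfusion related adverse events will be scored as 1+ vs. 0 and will be assessed via Chi"-square, against expected rates. Four reactions are listed, each with a reference range, and the higher incidence is to be used.
- **Secondary, item 1:** "Change in 7-point ordinal scale score and SOFA score over time will be assessed via individual" growth models, which makes two models.
- **Secondary, item 2:** "Mortality will be assessed via Chi-Square test with a hypothesized current mortality rate of 1-5" per cent.
- **Secondary, item 3:** need for ventilation, "assessed via Chi-Square test with a currently available published estimates".
- **Secondary, item 4:** three time or duration outcomes compared with published estimates, with no test named.

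Nowhere do the documents give a hierarchy, a multiplicity adjustment, or a statement that secondary results are descriptive. Target Recipient Recruitment is "150-200 individuals", with no derivation.

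**The concern.** The plan singles out one result as evidence of efficacy, then gives every other result the same label at the same threshold. A mortality, ventilation, SOFA or reaction result with p<0.05 could be reported as statistically significant with nothing to tell the reader that it was one of several. The chance that at least one such label is false is then well above the error of any one test.

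The reactions raise a second problem. Some reference rates are so low that only a fraction of an event is expected in the whole study. A chi-square test does not hold its 5% level there, so the label could be wrong for a single test even without multiplicity. At stake is a safety statement, such as an excess of lung injury, resting on one event.

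**Working it through.** **Inputs from the documents.** Two-sided threshold 0.05; 150 to 200 recipients; higher reference rates of 1:68 (circulatory overload), 1:1,200 (lung injury), 3% (allergic) and 1% (febrile). The plan gives no overall error rate and no power calculation, so there is no figure of its own to reproduce.

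**Step 1: count.** Day-7 model 1 + reactions 1 + growth models 2 + mortality 1 + ventilation 1 = 6. The wording on reactions can mean one pooled any-versus-none test or four tests. With four the count is 9.

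**Step 2: chance of at least one false positive, all nulls true.** For k independent tests this is 1 − 0.95^k:

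- k = 6: 1 − 0.7351 = 26.5%
- k = 9: 1 − 0.6302 = 37.0%

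Independence is not realistic here. Death and ventilation are categories of the same scale, and the day-7 model and one growth model use the same score. Simulating equally correlated two-sided normal tests (200,000 sets per setting; the correlations are assumptions) gives:

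| Correlation | 6 tests | 9 tests |
|---|---|---|
| 0 | 26.5% | 37.0% |
| 0.3 | 24.2% | 32.7% |
| 0.5 | 20.9% | 27.0% |
| 0.8 | 13.7% | 16.5% |

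**Step 3: does a single reaction test hold 5%?** With n units, reference rate p and x events, the statistic is X² = (x − np)² / [np(1 − p)], compared with 3.84. For lung injury, p = 1/1,200. Assume one unit per recipient:

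- n = 150: np = 0.125. One event gives 0.875² / 0.1249 = 6.13, p = 0.013.
- n = 200: np = 0.167. One event gives 0.833² / 0.1665 = 4.17, p = 0.041.
- No events gives X² = 0.13 and 0.17, not significant.

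The test therefore rejects as soon as one event occurs. Its true size is 1 − (1,199/1,200)^n, which is 11.8% at n = 150 and 15.4% at n = 200.

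The exact binomial sizes of the other reaction tests, at n = 150 and 200, are: overload 2.4% and 3.0%; allergic 4.8% and 5.6%; febrile 6.5% and 5.2%. A pooled any-reaction test, with reference 1 − (1 − 1/68)(1 − 1/1,200)(0.97)(0.99) = 5.5%, has size 4.6% and 4.1%. The clear failure is thus confined to lung injury tested on its own.

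**Step 4: dependence on the unit count.** The Dosing section allows up to three doses, so the units could reach 3 × 200 = 600. One event stays significant up to n = 211. Beyond that two are needed. At n = 300, np = 0.25, one event gives 0.75² / 0.2498 = 2.25, and the size is P(2 or more events) = 2.6%. At n = 600, np = 0.5, one event gives 0.50, two give 1.5² / 0.4996 = 4.50, and the size is 9.0%. The direction of the error changes with the denominator. The 5% label is unreliable throughout.

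**Step 5: what an exact interval would show.** The Clopper-Pearson lower limit for one event is 1 − 0.975^(1/n). The upper limit solves (1 − p)^n + np(1 − p)^(n−1) = 0.025. For 1/200 the interval is 0.01% to 2.75%; for 1/150 it is 0.02% to 3.66%. Both contain the reference rate of 0.083%, whereas the chi-square test calls each result significant.

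**The case against.** The strongest reply is that a threshold of 0.05 per analysis never promised 5% across the set, and that the plan ties evidence of efficacy to one test that also refers to a 2-point change. Both points stand. A reader might infer that the efficacy conclusion is itself inflated. It is not, because no secondary or safety result is given a success rule.

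A reader might also take 37% as the size of the problem. That figure needs four separate reaction tests, independence, and a 5% size for each. The plan's scoring of reactions as any versus none can well be read as one test, Step 3 shows that the separate tests do not all have 5% size, and correlation is likely. The six-test range is the fairer statement.

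A third tempting reading is that enrolment may be closed between 150 and 200 once a p-value turns favourable. The design is open-label, and Trial Methods mentions outcome monitoring, so looks at the data are possible. But the documents state no interim testing and no outcome-driven closure. A target range alone does not raise the error of any test.

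Finally, the lack of a control group is a larger threat: natural recovery or case mix can produce significance against day 0 or an outside rate. This is true, and no change proposed here repairs it. It is a further reason to prefer estimates with intervals to significance labels.

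**Conclusion.** The point holds as a defect in how results will be labelled, not as an error in the efficacy conclusion. Over the six analyses with a named method, the chance of at least one false significant result is about 14% to 26%. This assumes that all nulls are true, each test has 5% size, and a common correlation lies between 0.8 and 0; the correlations are not from the documents. Separately, if each reaction is tested by chi-square, the lung-injury test has a true size of 11.8% at 150 recipients and 15.4% at 200, on one unit per recipient. With more units the size moves below and then again above 5%. If reactions are pooled into one test, this second problem does not arise.

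**What to change.** Amend the Statistical Plan in three places:

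1. Reserve the term statistically significant for the day-7 primary efficacy test, which keeps its two-sided 0.05 unadjusted.
2. Replace the reaction chi-square tests with observed rates and exact (Clopper-Pearson) 95% confidence intervals, shown beside the listed reference rates. State whether the denominator is recipients or units.
3. Report secondary and exploratory results as estimates with 95% confidence intervals, and label any p-value nominal.

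The cost is a few sentences and no new data. The downside is that fewer results can be called significant. As an optional clarification only, the plan could add that the final number of recipients is set without sight of outcome summaries.

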| Renal Creatinine, mg/dL (μmol/l) or Urine output | Normal | 1.2-1.9 (110-170) | 2.0-3.4 (171-299) | 3.5-4.9 (300-440) or <500 mL/day | >5.0 (>440) or <200 mL/day |

26 * Source: [Vincent et al., 1996](#).

- 27 10) All other adverse and serious adverse events will be recorded as well (see adverse events section to follow).
- 28 11) Change in standard of care inflammatory markers (ferritin, LDH, CRP, D-dimer) where available
- 29 from day 0 to days 7, 14, 21, 28.

1 Exploratory Endpoints:

2 12) Association between antibody levels and donor characteristics/clinical course
3 13) Association between clinical response in recipients and antibody levels in the donors

4

5 **Dosing:**

6 • One dose of 200-300mL (standard collection bag volume) of convalescent plasma will be infused
7 over approximately one hour intravenously with standard vital sign monitoring per unit protocol
8 and standard of care for plasma infusion.

9 • Up to two additional doses of 200 mL of convalescent plasma may be administered within 14 days of initial
10 dose at 1-7 day intervals according to disease severity and tolerance of the infusions. Where possible,
11 plasma from distinct donors will be used for additional doses.

12 • To reduce probability of allergic reaction, pre-medication with diphenhydramine 25mg orally or
13 intravenously will be given within 2 hours before each dose of plasma, unless there is a
14 contraindication noted by treating physician.

15 • Slower infusion time of two hours with optional dose of 20mg intravenous furosemide after first
16 hour can be considered for patients at risk for transfusion-associated circulatory overload

17 • Infusion can be slowed for patient comfort at any time.

18 **Safety:** Patients will be monitored closely during plasma infusion per Inova nursing policy titled
19 “Transfusion/Infusion of Blood Components” Version 01.01. Patients will remain in the hospital for a minimum
20 of 24 hours post-infusion with vital signs performed per standard of care with frequency based on the
21 treating hospital unit. Patients will be discharged from hospital according to standard of care any time
22 after completion of 24 hour observation period post-infusion dosing.

23 If oxygenation worsens post-infusion, treating physician will perform assessment as to the presence of a
24 transfusion related reaction, increase oxygen delivery, and obtain portable chest film if deemed clinically

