25 appropriate. Treating physician will notify the study doctor and staff if there is an adverse reaction.

26 Possible anticipated infusion related reactions could include:

27 1) Transfusion Associated Circulatory Overload – dose of intravenous furosemide may be
28 considered
29 2) Transfusion-Related Lung Injury- supportive care as directed by treating physician
30 3) Allergic Reaction/Anaphylaxis – additional dose of diphenhydramine, dose of intravenous or oral
31 corticosteroids or intramuscular epinephrine could be considered
32 4) Transmission of transfusion transmitted diseases – supportive care or targeted treatment if
33 infection identified
34 5) Febrile Transfusion Non-hemolytic Transfusion Reaction – supportive care

35 These adverse events, if present, will be recorded by clinical research team.

36

37 **Post-Treatment Blood Draws:**

38 Optional blood draws (up to four tubes) may be drawn on days 7, 14, 21, and 28 (+/2 days) following each
39 dose of convalescent plasma where feasible for Biobanking.

40 If patient is discharged prior to 7 days post-dosing, then follow-up phone call or email assessments
41 will be made by study staff at 7 days, 14 days, 21, and 28 days (+/2 days) following the original dose.

1
2 **Script for Phone Call(s) or Email(s) to Recipients (if applicable):**

3 1) Are you in a home environment (your home or family member's home)?
4 2) If not, are you in a nursing or rehabilitation facility?
5 3) Are you using oxygen?
6 4) Have you required an urgent care or emergency room visit for any reason since your
7 discharge?
8 5) Have you required re-hospitalization for any reason since your discharge?

9
10 **Trial Methods**

11 Convalescent plasma will be made available to patients hospitalized in the Inova Heath System.

12
13 Patient outcome monitoring and reporting will include indicators of safety and efficacy. Case Report
14 Forms will be used to capture essential data.

15
16 **Statistical Plan**

17 Study parameters (e.g., clinical status scale, death, hospitalization, etc.) will be described using traditional
18 descriptive statistics (median [IQR], frequency and percent). Data will be assessed for 'missingness' with
19 parameters exceeding 10% missing explored for imputation (e.g., multiple imputation, last value carried
20 forward, etc.). Departures from normality will be assessed via Shapiro-Wilkes test with data

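### The primary efficacy rule treats an uncontrolled day 0 to day 7 rise in plasma recipients as evidence of efficacy, with no reference value and no stated null.

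*Combined protocol and SAP*

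**What the plan says.** The scale runs from 1 (death) to 7 (out of hospital), so a higher score is better (Primary Endpoints, item 1). In the Statistical Plan, Primary efficacy endpoints, item 1, a generalized linear mixed model compares day 0 with day 7. The decision rule is "A statistically significant increase of ± 2 points in β" "from day 0 to day 7 will be considered as evidence of efficacy". The general significance level is 0.05, two-tailed. Recipients form one open-label group with a target of 150 to 200, and no comparison group is described.

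The same section gives outside references for other endpoints:

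- Infusion reactions have listed expected incidences.
- For deaths: "Mortality will be assessed via Chi-Square test with a hypothesized current mortality rate of 1-5" percent, age adjusted.
- Need for ventilation is "assessed via Chi-Square test with a currently available published estimates", with no figure given.
- Time off oxygen, time off the ventilator and length of stay are also set against published estimates, again without figures: "duration of hospitalization will be summarized as median (IQR) or rates and compared to currently" available published values.

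None of these is tied to the 7-point rule. Neither is exploratory endpoint 13: "Association between clinical response in recipients and antibody levels in the donors".

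**The concern.** The Study Hypothesis is comparative: plasma should speed recovery, which means faster than without it. The rule has no such comparison. Patients are discharged by standard of care after a 24-hour observation period (Safety), and discharge puts a patient in category 7. That is a gain of 3 from category 4, 4 from category 3 and 5 from category 2. Entry covers both severe and life-threatening disease, so the mean change depends heavily on case mix and discharge practice.

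The rule also does not say what β is tested against. Three readings are possible:

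1. Any rise significant against 0.
2. A rise significant against 0 whose estimate is at least 2.
3. A rise significantly greater than 2.

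The same data can pass one reading and fail another, and the choice could be made after the results are seen. Because this is the only sentence in the plan that turns a result into a finding of efficacy, usual recovery could be credited to plasma, or a real gain dismissed.

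Two smaller ambiguities add to this, but the point does not rest on them. The ± sign conflicts with an increase. The model's link is also unstated, with "transformations explored as needed"; a 2-unit β is 2 score points only under an identity link. Under a cumulative logit it would be an odds ratio of exp(2) = 7.4.

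**Working it through.** The plan gives no power calculation, SD or expected change for this endpoint, so it has no figure of its own to reproduce. From the documents come n = 150 to 200, two-sided α = 0.05, the scale and the 2-point figure. Everything else below is assumed.

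**Observed mean rise needed.** On complete day 0 and day 7 data with an identity link, a random-intercept linear mixed model gives the paired mean change and its SE. This was confirmed on one simulated trial (n = 150: β 1.247, SE 0.141, equal to the paired values). So SE = SD/√n, and t is the 97.5% point with n − 1 degrees of freedom. SD is assumed to be 1.5 to 2.5.

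- Reading 1 needs t × SE: 0.21 (SD 1.5, n = 200) to 0.40 (SD 2.5, n = 150).
- Reading 2 needs 2.00.
- Reading 3 needs 2 + t × SE: 2.21 to 2.40.

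Reading 3 therefore asks for about 6 to 11 times what reading 1 asks for (2.40/0.40 = 6.0; 2.209/0.209 = 10.6).

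**How often the rule is met with zero plasma effect.** A patient starting in category s changes by 7 − s if discharged, 1 − s if dead and 0 otherwise. The mean rise is the sum over s = 4, 3, 2 of (share) × [(discharge rate)(7 − s) + (death rate)(1 − s)]. For the first row of the table: 0.5(0.70×3 − 0.02×3) + 0.3(0.35×4 − 0.08×2) + 0.2(0.05×5 − 0.20×1) = 1.02 + 0.372 + 0.01 = 1.40. Pass rates come from multinomial simulation at n = 150 and 200. Percentages are for categories 4/3/2.

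| Mix | Discharged by day 7 | Dead by day 7 | Mean rise (SD) | Reading 1 | Reading 2 | Reading 3 |
|---|---|---|---|---|---|---|
| 50/30/20 | 70/35/5 | 2/8/20 | 1.40 (1.83) | 100% | <0.1% | <0.1% |
| 50/30/20 | 85/60/15 | 2/8/20 | 2.03 (1.89) | 100% | 58–59% | 4% |
| 70/20/10 | 85/55/10 | 2/8/20 | 2.18 (1.68) | 100% | 91–94% | 28–34% |
| 30/30/40 | 30/15/5 | 5/10/25 | 0.35 (1.51) | 82–92% | <0.1% | <0.1% |
| 30/30/40 | 20/10/5 | 5/10/25 | 0.20 (1.36) | 40–52% | <0.1% | <0.1% |
| 20/30/50 | 20/10/3 | 5/10/25 | 0.10 (1.24) | 13–17% | <0.1% | <0.1% |

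**Favourable corner case.** If everyone starts in category 4 and nobody dies, the mean rise is 3 × the discharge rate, so an estimate of 2 means two thirds discharged. Exact binomial pass rates at 60%, 70% and 75% discharge are 2–6%, 84% and over 99% under reading 2. Under reading 3 they are <0.1%, 16–20% and 65–77%. Reading 1 passes 100% throughout.

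**A real effect missed.** Take the first row and let plasma add 10 percentage points of discharge in each category. The mean becomes 0.5(2.34) + 0.3(1.64) + 0.2(0.55) = 1.77. Reading 2 passes in 4–7% of trials and reading 3 in <0.1%. Reading 1 passes in 100%, with or without the gain.

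**The case against.** The strongest reply is that the 2-point bar is a real safeguard. Reading 1 ignores the 2 printed in the rule and is the least natural reading, yet it produces every 100% above. Under readings 2 and 3 a false pass needs untreated recovery near or above 2 points. The scenarios that reach this assume 85% discharge by day 7 from category 4, or a favourable all-category-4 group with no deaths, in a population selected for severe or life-threatening disease. Nothing in the documents supports those inputs. Reading 1 also passes less often in very sick mixes (13–17% in the last row). The simulation ignores moves between categories short of discharge or death. It also ignores the 24-hour stay and possible further doses, which tie discharge timing partly to the protocol. Finally, the trial is openly single-arm, and the background section explains why formal multicenter trials were not immediately feasible.

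Most of this stands as a limit on size. The false-pass risk depends on case mix, and under readings 2 and 3 it is small when untreated recovery is well below 2 points. It does not rescue the rule. The plan never commits to a reading and never justifies 2 points as more than patients would gain without plasma. Readings 2 and 3 alone can differ as widely as 58–59% against 4%. Even 13–17% is far above the 2.5% that a two-sided 5% test allows in the direction of benefit. Running a single arm is defensible; calling its before-after change evidence of efficacy is not.

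**Conclusion.** The concern holds and should be fixed before analysis. The conclusion rests on the text: a recipients-only, time-only contrast, no expected untreated change, no stated null, and an explicit efficacy label. It does not depend on the simulations, whose inputs are all assumed. They show what is at stake. With no plasma effect, the chance of declaring efficacy ranged from under 0.1% to 100%, depending on the reading and on background recovery. A 10-point gain in discharge could pass as rarely as <0.1% or as often as 100%. No reading separates a plasma effect from usual recovery. The other efficacy information in the plan does not enter this rule.

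**What to change.** Replace the decision sentence in Primary efficacy endpoints, item 1, with wording such as:

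> The mean day 0 to day 7 change on the 7-point score (positive = improvement) will be estimated from the mixed model on the score scale (identity link) with a two-sided 95% CI, and the day-7 category distribution will be tabulated by day-0 category. Within-arm change is descriptive and is not by itself evidence of efficacy.

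If the 2-point figure is kept, write it as +2, say whether it is a minimum estimate (null 0) or the null value itself, and call it a descriptive benchmark.

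The mixed model, sample size and data collection stay as planned. The plan already provides "descriptive statistics (median [IQR], frequency and percent") for the scale, so only the split by day-0 category is new. The cost is a more modest claim. The mean also treats the seven categories as evenly spaced, which is why the category table goes with it.

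### The test of transfusion reactions does not fix its unit of analysis or the number of tests: on a per-patient score the per-unit circulatory-overload rate is the wrong null once doses repeat, and uncorrected chi-square fails for lung injury if events are tested separately

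*Combined protocol and SAP*

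**What the plan says.** The Statistical Plan (Primary efficacy endpoints, item 2) gives the whole method in one sentence: "Plasma transfusion related adverse events will be scored as 1+ vs. 0 and will be assessed via Chi"-"Square test with a hypothesized distribution of expected AE (using the higher incidence estimate"). The significance rule, stated for all analyses, is "with p<0.05, two-tailed considered statistically significant". Four reference ranges follow. Only the first has a denominator: "Transfusion Associated Circulatory Overload: 1:1,566 to 1:68 plasma units" transfused. The next is "Transfusion-Related Lung Injury: 1:1,200 to 1:190,000", with none. Allergic reaction is put at 1-3% and febrile non-hemolytic reaction at 0.1-1%, also with none.

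Under Primary Endpoints, item 2, the reactions form one numbered endpoint, counted within six hours of infusion. It lists five events; the fifth, transmission of transfusion-transmitted disease, has no reference rate in the Statistical Plan.

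On exposure, the Dosing section says "One dose of 200-300mL (standard collection bag volume) of convalescent plasma will be infused", then "Up to two additional doses of 200 mL of convalescent plasma may be administered within 14 days of initial" dose. Target Recipient Recruitment is "150-200 individuals".

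The documents do not say whether the score belongs to a patient, an infusion or a unit, or whether the four rates feed one test or four. They mention neither an exact test nor a continuity correction.

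**The concern.** The plan describes no control group for this endpoint, so the reference rate is the only comparator. If numerator and null use different denominators, the test compares unlike quantities: a patient given two units has two chances of a reaction, but would be judged against the risk of one. That pushes the result towards an apparent excess of harm. Separately, a chi-square approximation is unsafe when far fewer than one event is expected, as for TRALI.

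A significant excess on a named primary safety endpoint would probably be read as harm from the plasma. While the unit and the number of tests stay open, that reading depends on choices that could be made after the data are seen.

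**Working it through.** The plan gives no expected count, power or error rate for this endpoint, so there is no figure of its own to reproduce. The check uses its inputs.

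**Inputs.** From the Statistical Plan: upper rates 1/68 (TACO), 1/1,200 (TRALI), 3% (allergic), 1% (febrile); two-tailed 0.05. From Target Recipient Recruitment: n = 150 to 200. From Dosing: one to three doses.

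**Assumptions.** One dose is one unit. Events are independent between doses and between event types; shared susceptibility within a patient would lower the repeat-dose figures. The share of patients re-dosed is not given, so a range is shown.

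**1. Per-patient TACO null.** The risk over k units is 1-(67/68)^k:
- k = 1: 1.47%
- k = 2: 2.92%
- k = 3: 4.35%

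At n = 150 the flat null expects 150 × 1.47% = 2.2 cases; two units each would give 150 × 2.92% = 4.4.

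**2. Rejection threshold.** The uncorrected one-sample chi-square is (x-np)²/[np(1-p)], with critical value 3.84. For TACO at n = 150, np = 2.206 and np(1-p) = 2.173. Five cases give 3.59 and six give 6.62, so six reject. At n = 200 seven reject. For a pooled any-event test with TACO at one unit, the null is 1-(67/68)(1199/1200)(0.97)(0.99) = 5.46%, and the thresholds are 14 and 18.

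**3. False harm signals.** These are exact binomial upper-tail probabilities, with true TACO risk 1/68 per unit and the other rates per patient at their upper values. Each range covers every n from 150 to 200.

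| Units received | Separate TACO test | Pooled any-event test |
|---|---|---|
| One each | 2.3-6.1% | 2.3-4.3% |
| 20% get a second | 5.0-11.7% | 3.4-6.1% |
| Half get a second | 11-23% | 5.6-9.8% |
| All get a second | 28-47% | 11-19% |

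**4. Sensitivity to the true rate.** At 1/136 per unit, two units give 1-(135/136)² = 1.47%, which is back at the flat null. At the geometric midpoint of the plan's range, √(1/68 × 1/1,566) = 0.31% per unit, with everyone given two units, the upper-tail rate is at most 0.12%.

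**5. TRALI tested separately, per patient.** The expected count is 150/1,200 = 0.125 to 200/1,200 = 0.167. One case gives:
- n = 150: (1-0.125)²/0.1249 = 6.13, p = 0.013
- n = 200: (1-0.167)²/0.1665 = 4.17, p = 0.041

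So one case rejects. Its chance under the null is 1-(1199/1200)^n = 11.8% to 15.4%. With a continuity correction one case gives p = 0.29 to 0.41 and does not reject.

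On a unit denominator the uncorrected false-signal rate is erratic: 16.1% at 211 units, 1.4% at 212, 2.6% at 300, 4.5% at 400 and 9.0% at 600.

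**The case against.** The strongest reply is that the wording leans away from the bad cases. The sentence is in the singular and the reactions form one endpoint, which suits a pooled test. At one unit each that test has an upper tail of 2.3-4.3% and a two-sided total of 3.1-5.9%, so there is no defect; with 20% re-dosed it stays near 5%. The six-hour window fits scoring by infusion, which with one unit per dose already matches the TACO denominator. Extra doses are optional. The plan uses the top of a 23-fold range (1,566/68), so the true rate may lie well below the null. No documented decision follows from the test, and raw frequencies would be reported beside it.

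All of this stands, and it limits the point. A reader might infer that the plan carries a 28-47% false-alarm rate. That needs per-patient scoring, a separate TACO test, a second unit for everyone and a true rate at the ceiling; the documents establish none of these. A reader might also infer four uncorrected tests with a 19-26% chance of some harm signal at one unit each, or a general failure of chi-square for TRALI. The number of tests is not stated, a continuity correction removes the TRALI result, and a pooled test does not have that problem.

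What the reply does not remove is that the plan never chooses among these readings, and on a per-patient score the flat 1/68 is wrong for anyone given more than one unit, pooled or not.

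**Conclusion.** The point holds conditionally and should be fixed; its severity is modest.

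It is confirmed that the unit of analysis and the number of tests are missing. If scoring is per patient, the TACO null is too low for re-dosed patients: by a factor of about two at two units (2.92/1.47) and about three at three (4.35/1.47). The effect on error rates is nil at one unit each, grows with the share re-dosed, is smaller in a pooled test, and largely disappears if the true rate is well below 1/68. It is also nil if scoring is per infusion with one unit per dose.

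The TRALI failure is narrower. It needs separate tests, per-patient scoring and no continuity correction together.

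The conclusion rests on one dose being one unit and on independence between doses. The denominators of the other three rates are not stated; if they too are per unit, the same mismatch applies to them.

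**What to change.** 1. State the unit of analysis, the denominator of each reference rate, and whether there is one test or four.
2. For TACO, and any other rate that is per unit, use units transfused as the denominator; or, if the per-patient score is kept, use each patient's own 1-(1-p)^k.
3. For separately tested events, use an equal-tailed exact binomial (or Poisson) test with an exact 95% confidence interval, always reported with the raw count. One TRALI case at 150-200 counts then gives p = 0.24 to 0.31, twice the 11.8-15.4% tail. An exact test alone is not enough: with the flat per-patient null, a TACO test still signals 16-33% of the time if all get two units.
4. A single pooled test may stay chi-square if its null is matched to units received.
5. Report transmission of transfusion-transmitted disease descriptively, since it has no reference rate.

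**Cost.** SAP wording and a few lines of code. Units per recipient must be captured; the documents do not say that the case report form does so. Counting by units assumes independence between one patient's units.

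The real price is sensitivity. Events needed for a harm signal, chi-square then exact:

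| Event | n = 150 | n = 200 |
|---|---|---|
| TACO | 6, 6 | 7, 8 |
| TRALI | 1, 2 | 1, 2 |
| Allergic | 9, 10 | 11, 12 |
| Febrile | 4, 5 | 5, 6 |

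If true TRALI risk were ten times the reference, the chance of a signal would fall from 71% to 36% at n = 150 and from 81% to 50% at n = 200. Counted over 300-600 units, TRALI needs three cases rather than two. Always reporting the count and interval keeps a single case visible.
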